10.3 EFFICACY ANALYSIS

10.3.1 Primary Efficacy

The primary endpoint of the study is the percentage change in target ulcer area over the 12-week treatment period and will be analyzed as follows. An initial linear regression model will contain covariates for treatment, center, wound type, baseline (defined as Study Visit 1) target ulcer area and duration of target ulcer. For purposes of the primary analysis, any centers with less than 10 subjects will be pooled. A forward selection procedure will be used for the addition of other baseline covariates with an F-value to attain a significance level of 0.1. Further baseline covariates to be assessed as part of this procedure include: subject age, body mass index, baseline ulcer depth, ABI and baseline level of exudate. The resulting primary analysis presented will correspond to the final model from the forward selection procedure. The results for the initial model will also be presented. For each of the effects in the initial and final model, the p-value, parameter estimate and corresponding 95.4% confidence interval will be presented.

Secondary subgroup analyses may be conducted as a result of the covariate analyses. Additionally, treatment will be fitted on its own in a further linear regression model. The potential for interactions, particularly treatment by center interactions will be examined by fitting the required interaction terms in addition to those effects in the final linear regression model from the forward selection procedure.

Non-inferiority will be concluded in each case if the upper bound of the 95.4% confidence interval for the parameter estimate relating to treatment covariate (coded as tNPWT – PICO) is less than ($<$) 12.5 which relates to the desired one-sided test at the 2.5% significance level after adjusting for the interim analysis.

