3. STATISTICAL CONSIDERATIONS

3.1 DETERMINATION OF SAMPLE SIZE

The study is intended to test for non-inferiority in the percentage change in target ulcer area between PICO and tNPWT over a 12-week treatment period. During a review of five previous studies with venous leg ulcer and diabetic foot ulcer, with treatment of PICO or tNPWT, the mean percentage change in ulcer area was found to be approximately between 47-62%, in cases where it was considered an appropriate measure, the standard deviation ranged approximately between 21-24.5%. Using a non-inferiority margin of 12.5%, a sample size of 128 subjects will provide 80% statistical power at the (cumulative) 0.025 one-sided significance level assuming a weighted average mean healing of 60% with a worst case standard deviation of 24.5%. This was calculated using EAST 6. To allow for a 20% drop out rate throughout the 12-week treatment period, a total of approximately 160 subjects (80 per treatment) will be randomized.

The sample size randomized will include a minimum of 100 VLU to allow for a minimum of 70% power for VLU-only analysis using the above assumptions.

An interim analysis (built into the sample size) of key variables will take place after approximately 50% of target recruitment (80 subjects completed) with the stipulation that the interim will contain at least 40 VLU and 20 DFU. A recommendation may be made at this point to stop the trial prematurely due to efficacy or futility.

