4.9 Primary Variable

The primary objective of the study is to compare PICO against ActiV.A.C.® in terms of the percentage change in the target ulcer area, over the 12-week treatment period.

Primary Analysis

An initial linear regression model will contain covariates for treatment, center, wound type, baseline (defined as Run-In Visit 2/Study Visit 1) target ulcer area and duration of target ulcer. For purposes of the primary analysis, any centers with less than 10 subjects will be pooled. A forward selection procedure will be used for the addition of other baseline covariates with an F-value to attain a significance level of 0.1. Further baseline covariates to be assessed as part of this procedure include: subject age, body mass index, baseline ulcer depth, ABI and baseline level of exudate. The resulting primary analysis presented will correspond to the final model from the forward selection procedure. The results for the initial model will also be presented. For each of the effects in the initial and final model, the p-value, parameter estimate and corresponding 95.4% confidence interval will be presented.

Non-inferiority will be concluded if the upper bound of the 95.4% confidence interval for the parameter estimate relating to treatment covariate (coded as ActiV.A.C.® – PICO) is less than ($<$) 12.5 which relates to the desired one-sided test at the 2.5% significance level after adjusting for the interim analysis.

If distributional and model assumptions relating to the above analysis do not hold, a permutation test will be used as a non-parametric non-inferiority analysis. The sampling distribution of the test statistic will be estimated by re-randomization of treatments to each of the study subjects. At a minimum the completed re-randomization process will be repeated 2000 times. However, if 2000 replicates are found to be insufficient for the random variation in results of successive repeats to be reduced to an acceptable level, the number of replicates will be increased until such a point as consistent results are observed between successive repeats of the permutation tests up to a maximum of 10,000 replicates.

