For purposes of the permutation analysis, to test against the null one-sided hypothesis of a difference greater than delta, the non-inferiority margin (delta=12.5%) will be added to, or subtracted from, the observed change in individual area measurement for those subjects that are re-randomized by the permutation test to the treatment which they were not randomized to during the trial. The resulting p-value will be derived as per usual bootstrapping techniques.

The primary analysis will be performed using the Per Protocol Population; the analysis will also be repeated using the Full Analysis Set. Differences in conclusions between the two analyses will be investigated. The ability to switch between non-inferiority and superiority will be considered only if both subject populations demonstrate non-inferiority.

Secondary Analysis

Secondary subgroup analyses may be conducted as a result of the covariate analyses. Additionally, treatment will be fitted on its own in a further linear regression model. The potential for interactions, particularly treatment by center interactions will be examined by fitting the required interaction terms in addition to those effects in the final linear regression model from the forward selection procedure.

The baseline area, final area, absolute change in area and percentage change in ulcer area over the 12-week treatment period will be summarized separated by treatment, centre, wound type and area used for stratification purposes (large/small) and baseline area (<median/>=median). Further summaries will be produced separated by the covariates used in the final model. The ulcer area, change in area and percentage change in area will be summarized by Study Visit (2-12) and

treatment, centre, wound type and area used for stratification purposes (large/small). Summaries will utilize the Per Protocol Population and will be repeated for the Full Analysis Set.

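### The primary model is chosen by forward selection, with nothing holding its covariates constant between the Per Protocol and Full Analysis sets; one fixed covariate list would cost little

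*SAP*

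**What the plan says.** SAP 4.9 and Protocol 10.3.1 describe the same procedure. An initial linear regression contains treatment, center, wound type, baseline ulcer area and ulcer duration. Then, in the Protocol's words, "A forward selection procedure will be used for the addition of other baseline covariates with an F-value to attain a significance level of 0.1". The named candidates are age, BMI, baseline depth, ABI and exudate level. The SAP is explicit about which model counts: "The resulting primary analysis presented will correspond to the final model from the forward selection procedure". The initial model is reported too, but not as the primary result. Non-inferiority is read from the upper 95.4% limit against 12.5.

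The primary analysis uses PP and is repeated in FAS. Protocol 10.3.1 refers the repeat back to everything in its preceding paragraphs, and those include the selection. Neither document says that covariates chosen in one set carry over to the other. If the sets disagree, "Differences in conclusions between the two analyses will be investigated" (SAP 4.9). Both sets must show non-inferiority only before a switch to superiority is considered. For the interim, SAP 3.3 and Protocol 11 give Z bounds but name no model.

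**The concern.** The covariates of the decisive model are unknown until the outcomes have been analysed. Three things follow.

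- PP and FAS estimates may be adjusted for different variables. Any investigation of a difference between them then has to separate population from adjustment.
- The interval is computed as if the chosen model had been fixed in advance. Selection favours candidates that happen to fit, so the interval comes out slightly too narrow.
- ABI is a candidate, yet Protocol 7.2 and 9.1.1 let arterial supply be confirmed by other tests when ABI is out of range or cannot be done. No rule for missing covariates is given. If ABI enters the model, the subjects analysed may change along with the adjustment.

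What is at stake is the pre-specification and readability of the primary result, more than the error rate itself.

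**Working it through.** **The design figure.** SAP 3.1 states that "a sample size of 128 subjects will provide 80% statistical power at the (cumulative) 0.025 one-sided significance level". Its other inputs are "Using a non-inferiority margin of 12.5", "worst case standard deviation of 24.5" and "assuming a weighted average mean healing of 60", the last taken as equal in both arms.

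- Fixed design: n per arm = 2 × (1.960 + 0.842)² × 24.5² / 12.5² = 60.3, so 61 per arm and 122 in total.
- Two looks with 128 subjects, half the information at the interim, bounds 2.963 and 0.559, and a final Z of 1.969 (an assumption): power 80.2%, one-sided alpha 0.0250.
- "To allow for a 20% drop out rate throughout the 12-week treatment period": 128 / 0.8 = 160.

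The stated design reproduces. The final test level is (1 − 0.954) / 2 = 0.023.

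**Simulation of the final analysis.** There were 100,000 trials per scenario. Forward selection was run separately in PP and in the FAS that contains it. In PP it was compared with the initial model and with a fixed model holding all five candidates. Assumptions not in the documents: FAS 156; PP 128 (range 110–145); 8 pooled center levels; forced covariates explaining 10% of variance; exudate as a 1-df score; candidates correlated 0.2 and explaining 0–22% of variance; PP exclusions at random. Type I error and power are given as selected / all-five fixed / initial.

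| Candidates (variance explained) | PP / FAS | Covariates differ | Type I error | Power, % |
|---|---|---|---|---|
| None prognostic (0%) | 128 / 156 | 31% | 0.0242 / 0.0226 / 0.0226 | 80.9 / 79.2 / 80.9 |
| Five weak (9%) | 128 / 156 | 54% | 0.0272 / 0.0236 / 0.0237 | 83.7 / 83.1 / 80.8 |
| Three moderate (12%) | 128 / 156 | 42% | 0.0256 / 0.0232 / 0.0235 | 85.2 / 84.4 / 80.6 |
| Two strong (22%) | 128 / 156 | 23% | 0.0243 / 0.0232 / 0.0226 | 89.3 / 88.5 / 80.8 |
| None prognostic (0%) | 145 / 156 | 20% | 0.0242 / 0.0228 / 0.0227 | 85.7 / 84.4 / 85.8 |
| Five weak (9%) | 110 / 156 | 67% | 0.0262 / 0.0224 / 0.0228 | 76.8 / 75.8 / 73.6 |

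- *Error rate.* The excess runs from 0.0242 − 0.023 = 0.0012 to 0.0272 − 0.023 = 0.0042. The Monte Carlo standard error is √(0.023 × 0.977 / 100,000) = 0.0005. Four scenarios of a 10,000-trial subject-level check (standard error 0.0015) gave 0.0212–0.0278 for selection, each above its own all-five counterpart.
- *Noise covariates.* Five independent null candidates would add at least one covariate in 1 − 0.9⁵ = 41% of trials. The simulation, with correlated candidates, gave 39%.
- *Power, selected minus all-five fixed.* From 83.65 − 83.09 = 0.6 to 80.92 − 79.15 = 1.8 points. Part of this is not real precision. In the weak scenario at 128 the selected estimate is more variable (empirical SD 4.258 against 4.215) and still shows the higher power.
- *Power, all-five fixed minus initial, at 128.* −1.7, +2.3, +3.8 and +7.7 points down the table.

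**Do the differing models change conclusions?** The table below gives the share of trials, with no true difference, in which PP and FAS disagree on non-inferiority.

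| Simulation | Selection | All-five fixed |
|---|---|---|
| Subject-level check, four scenarios | 8.8, 14.1, 4.2, 5.8% | 9.5, 14.7, 4.7, 6.2% |
| PP 128 of FAS 156, two scenarios | 11.1, 11.7% | 12.3, 11.9% |
| 160 randomized, 20% excluded from PP, three scenarios, 3,000 runs each | 13.0, 12.1, 10.6% | 14.0, 11.8, 10.4% |

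In the last simulation, carrying the PP-selected covariates over to FAS gave 13.0, 11.8 and 10.3%. Agreement between the sets hardly depends on whether the model is selected or fixed.

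**The case against.** The best defence is that the rule is an algorithm. The core covariates and treatment are always in, the candidates are named, and nothing is screened on the treatment effect. Selection is slightly more powerful than a fixed list, the error rate barely moves, and the two sets agree about as often either way. All of this stands. There is also some slack. The two-look calculation reached a cumulative 0.0250 with a final Z of 1.969, which is one-sided 0.0245. A final-look error of 0.0242 is still within that, while 0.0272 exceeds it by 0.0027.

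Rerunning the selection in FAS is also a reading. SAP 4.9 says only that the analysis is repeated and speaks of one final model. The Protocol's wording supports a rerun more clearly.

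Four stronger readings are tempting, and the documents do not support them.

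- *The sponsor could decide the trial by choosing which model to read.* At 128, the selected and initial models disagree in PP in 1.7–11.8% of trials with no true difference. But SAP 4.9 names the selected model as primary. The disagreement also comes mostly from adding covariates at all: in the 3,000-run simulation, initial versus selected differed in 2.1, 6.8 and 9.8%, and initial versus all-five fixed in 4.8, 7.5 and 10.0%.
- *PP and FAS are jointly decisive.* PP is primary; both are required only for the switch to superiority.
- *Selection is rerun at the interim.* The documents are silent on the interim model, and silence is not an instruction.
- *Selection gains nothing.* Against the initial model it gains 2.9 (83.7 − 80.8) to 8.5 (89.3 − 80.8) points at 128 when candidates are prognostic. Only against a list containing the candidates is the gain small.

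**Conclusion.** The point holds as a weakness of pre-specification with a small numerical effect. As written, the PP and FAS models would often adjust for different covariates (about 20–67% of simulated trials), and the 95.4% interval has one-sided error of about 0.024–0.027 instead of 0.023. The effect on agreement between PP and FAS conclusions is negligible. The frequencies rest on the assumed set sizes, prognostic strength and random PP exclusions, hence the ranges. The textual finding, that nothing holds the covariates constant, does not depend on them. Severity: minor to moderate.

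**What to change.** In SAP 4.9 and Protocol 10.3.1, make one fixed covariate list primary: the initial model plus age, BMI, baseline depth and exudate as a 1-df score. State that it is used unchanged in PP, FAS and the interim. Report the forward-selected model as a sensitivity analysis.

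Leave ABI out, because arterial supply may be confirmed by other tests and some subjects may have no value. SAP 4.10 already omits ABI from the candidates for closure and time to closure. The other four covariates are collected by schedule, but the documents do not guarantee that they are complete, so add a rule for missing values. The key secondary analyses repeat the primary procedure and need the same wording; in the depth model, baseline depth is already included.

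The cost is a wording change and about 0.5–2 power points relative to selection, part of which reflects selection's slightly raised type I error. When candidates are prognostic, the fixed list has more power than the initial model alone; when none is, it has up to 1.7 points less at 128. These figures are for the list with all five candidates. The four-covariate list was not simulated, and it gives up whatever ABI would explain.

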2. STUDY DESIGN

2.1 DESCRIPTION OF TRIAL DESIGN

This is a multi-center, Phase 4, randomized, open-labelled, comparative-effectiveness study in subjects with at least one lower extremity wound (VLU or DFU). Subjects will be randomized to one of two treatment groups to receive either PICO single-use NPWT system or ActiV.A.C. ® System, for 12 weeks, or until target ulcer closure (by surgical intervention or secondary intention), whichever occurs first.

The study consists of four periods: a 1-week run-in period (including screening Run-In Visit 1, Run-In Visit 2), a 12-week randomized treatment period (including Study Visit 1 through Study Visit 12), a 1-week end-of-treatment assessment period (including Study Visits 13, 14). Study Visit 14 serves as the end of study visit.

Following a 1-week run-in period, approximately 160 subjects meeting entry criteria will be randomly assigned to one of the two treatment arms in a 1:1 allocation ratio to receive treatment with either PICO single-use NPWT system or ActiV.A.C. ® system for 12 weeks with dressing changes as deemed required in the opinion of the investigator or required in the instructions for use (IFU).

Eligible subjects will receive treatment for 12 weeks (Visits 1 through 12), or until their wound closes or progressing sufficiently to become ready for surgical closure in the opinion of the investigator. Subjects whose wounds have closed, as assessed by the Investigator, prior to the 12th week of treatment (or Visit 12) will stop treatment and return for one further visit (Visit 14) to verify if the target ulcer remains closed for one week following the initial observation of ulcer closure. An ulcer which remains closed at this one week verification assessment is defined as having achieved complete wound closure in this study.

For those subjects who are randomized and who discontinue from the study prior to Visit 13 due to any reasons other than target wound closure, Visit 14 will serve as the early termination (ET) visit.

The size of the target ulcer, pain associated with target ulcer will be assessed for each subject at Run-In Visit 1 (screening). This information, along with the status of

Document Number: 1004313
Document Version: 06

Document Part: 000
Document Status: Released

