3.2 RANDOMIZATION

All eligible subjects will be randomized between PICO and ActiV.A.C.[®] therapy settings by means of an online randomisation system (Sealed Envelope).

Treatment will be randomized, stratified by wound type and wound size at the conclusion of the screening period (and prior to commencement of the treatment period) to prevent imbalance on these variables between the two treatment groups.

The resulting strata will be as follows:

- *Small DFU ($\leq 2 \text{ cm}^2$)*
- *Large DFU ($> 2 \text{ cm}^2$)*
- *Small VLU ($\leq 12 \text{ cm}^2$)*

- Large VLU (>12 cm²)

A blocked randomization will be used for each stratum utilizing a block size of 2 and 4. Due to visible differences between treatments, allocation to treatment will not be blinded.

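### The fallback permutation test is not tied to the four randomization strata and its test statistic is not named; stating both is a free improvement

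*SAP*

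**What the plan says.** SAP 3.2 stratifies allocation into small and large DFU (cut at 2 cm²) and small and large VLU (cut at 12 cm²): "A blocked randomization will be used for each stratum utilizing a block size of 2 and 4".

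SAP 4.9 makes a linear regression the primary analysis, with treatment, center, wound type, baseline area and ulcer duration in the initial model. The decision rule begins "Non-inferiority will be concluded if the upper bound of the 95.4% confidence interval for the parameter estimate relating to treatment covariate" and requires that bound to lie below 12.5. If the distributional or model assumptions do not hold, a permutation test takes over: "The sampling distribution of the test statistic will be estimated by re-randomization of treatments to each of the study subjects". The 12.5 margin is added or subtracted for subjects whose treatment switches in a re-randomization. Protocol 10.3.1 has the same text.

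Neither section says whether the re-randomization is free or follows the strata and blocks. Neither says whether the statistic is a raw difference in means or the adjusted treatment coefficient. The depth and volume analyses repeat the primary analysis (SAP 4.10), and SAP 3.3 moves the interim bounds to the p-value scale if normality fails.

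**The concern.** A re-randomization test is calibrated to the design when it repeats the allocation that was used. Blocking within strata keeps the arms nearly balanced on wound type and size, so little between-stratum variance enters the observed treatment difference. A free permutation generates allocations unbalanced on those factors and puts that variance back into the reference distribution. With an unadjusted statistic and prognostic strata, the distribution is wider than the real sampling variation.

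The fallback could be needed. Closed ulcers are imputed as 0 cm² and so pile up at 100% reduction, while enlarging ulcers form the opposite tail. What is at stake is power in the analysis that would then decide the trial. There is also a reproducibility issue: two analysts following the same text could permute differently, use different statistics and report different p-values.

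**Working it through.** **Inputs.** From SAP 3.1: "128 subjects will provide 80% statistical power at the (cumulative) 0.025 one-sided significance level"; "weighted average mean healing of 60% with a worst case standard deviation of 24.5"; "Using a non-inferiority margin of 12.5"; "To allow for a 20% drop out rate throughout the 12-week treatment period". From SAP 2.1: "randomly assigned to one of the two treatment arms in a 1:1 allocation ratio". From SAP 4.9: a 95.4% interval, so the final one-sided level is (1 − 0.954)/2 = 0.023 and c = 1.995. The true difference is 0.

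**The plan's own figure.** A fixed design needs 2 × (1.960 + 0.842)² × 24.5² / 12.5² = 60.3, so 61 per arm or 122 in total. Adding the interim at half the information (efficacy bound 2.963, futility bound 0.559 obeyed, final bound 1.969) gives 80.2% power at N = 128, with cumulative one-sided error 0.0250 when futility is ignored. Then 128/0.80 = 160. The stated size reproduces. Using 1.995 as the final bound gives 79.6%; that shift comes from the bound, not from the permutation scheme.

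**Assumption.** R² is the share of outcome variance explained by the four strata, and the documents do not give it. The only anchor is the 47–62% spread of mean changes across the earlier studies. If VLU and DFU sat at opposite ends of it, in the 100:46 ratio of the recruitment minima, wound type alone would give R² = (100/146)(46/146) × 15²/24.5² = 0.08. I range R² from 0 to 0.30.

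**Formulas, unadjusted difference in means, interim ignored.**
- SE₀ = 24.5 × √(4/128) = 4.331, and z = 12.5/4.331 = 2.886.
- s = √(1 − R²). The true SE under stratified allocation is s × SE₀; a free permutation still uses SE₀.
- Free: power = Φ((z − c)/s), true error = 1 − Φ(c/s).
- Within strata: power = Φ(z/s − c), error 0.023.

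Example at R² = 0.20, s = 0.8944:
- Free power: (2.886 − 1.995)/0.8944 = 0.996, so 84.0%.
- Within-strata power: 2.886/0.8944 − 1.995 = 1.232, so 89.1%.
- Free true error: 1.995/0.8944 = 2.231, so 0.0128.

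| R² | Reference width, free (ratio to true) | Power, free | Power, within strata | True error, free |
|---|---|---|---|---|
| 0 | 1.00 | 81.3% | 81.3% | 0.023 |
| 0.08 | 1.04 | 82.4% | 84.5% | 0.0187 |
| 0.20 | 1.12 | 84.0% | 89.1% | 0.0128 |
| 0.30 | 1.20 | 85.7% | 92.7% | 0.0085 |

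**Simulation check.** 3000 trials, 800 permutations each, blocks of 2 and 4, assumed stratum sizes 46/34/24/24, the SAP's margin shift, one-sided 0.023. Power, free v within strata:

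| R² | Unadjusted | Adjusted for wound type and baseline area |
|---|---|---|
| 0 | 80.5% v 80.5% | 79.8% v 80.0% |
| 0.08 | 81.1% v 83.3% | 82.2% v 82.9% |
| 0.20 | 82.9% v 88.6% | 87.8% v 88.1% |
| 0.30 | 85.7% v 91.9% | 91.4% v 91.9% |

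The Monte Carlo standard error is about √(0.8 × 0.2/3000) = 0.7 points per entry. Skewed errors give the same pattern (R² 0.20: 82.9% v 88.0% unadjusted, 87.3% v 87.5% adjusted). Simulated error for the free, unadjusted test at R² 0.08 was 0.0187, as in the formula; the error figures at 0.20 and 0.30 are analytic only.

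**The case against.** The strongest reply is that the text does not prescribe a free permutation. To re-randomize can mean to repeat the trial's own process, which SAP 3.2 defines as stratified and blocked. That is fair: free permutation is the literal reading, not a stated rule. The literal reading has some support, since Protocol 10.3.2 expressly stratifies the rank-sum test for quality-of-life changes and the permutation text has no such words.

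Second, the loss needs an unadjusted statistic. The test replaces a regression that already contains wound type and baseline area, so the adjusted coefficient is a natural candidate, and with it the scheme hardly matters. This stands, and it is why the statistic must be named.

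Third, R² is unsupported. At the only available anchor, 0.08, the loss is about 2 points; at 0 there is none. This also stands.

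A reader might go further and infer that the fallback test is invalid, or that the trial becomes underpowered. The figures do not support that. Since z exceeds c, dividing (z − c) by s below 1 only raises free power above 81.3%, and c/s above c only lowers the error. The sample size uses the full SD of 24.5 and takes no credit for stratification, so no planned power depended on it. Nor do the documents give any figure for how likely the regression assumptions are to fail.

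**Conclusion.** The point holds as a free improvement. The plan stratifies the allocation but does not carry the strata into the fallback test, and it leaves the test statistic open. If the permutation is free and the statistic unadjusted, the cost against a within-strata permutation is about 2 points of power at R² 0.08 (84.5 − 82.4), 5 at 0.20 (89.1 − 84.0) and 7 at 0.30 (92.7 − 85.7), with true one-sided error falling to 0.019, 0.013 and 0.0085. It is nil at R² 0 and under 1 point with an adjusted statistic. The error is in the conservative direction, and the permutation scheme does not bring power below the planned 80%. All of this rests on assumed R², ignores the interim, and matters only if the regression assumptions fail.

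**What to change.** In SAP 4.9 and Protocol 10.3.1, state that treatments are re-randomized within each of the four randomization strata, respecting the blocks as far as the analysis set allows, and that the test statistic is the stratum-weighted or covariate-adjusted treatment difference after the 12.5 shift. The qualification on blocks is needed because the primary population is Per Protocol, and its exclusions leave some blocks incomplete. Apply the same rule to the depth and volume analyses and to the interim p-value.

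The cost is one sentence in each document and a stratum loop in the program. No extra subjects or data are needed.
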